7.6.12.4 Additional Analyses

In addition, the following analyses on specific laboratory parameters will be performed for all treated subjects, by cohorts and SRT status:

Abnormal Hepatic Function Test

The number of subjects with the following laboratory abnormalities from on-treatment evaluations will be summarized:

- ALT or AST > 3 x upper limit of normal (ULN), > 5 x ULN, > 10 x ULN and > 20 x ULN
- Total bilirubin > 2 x ULN
- Concurrent (within 1 day) ALT or AST > 3 x ULN and total bilirubin > 2 x ULN
- Concurrent (within 30 days) ALT or AST > 3 x ULN and total bilirubin > 2 x ULN

The following scatterplots will be produced for the following hepatic laboratory parameters:

- Total bilirubin peak vs. AST peak
- Total bilirubin peak vs. ALT peak

On-treatment peak total bilirubin and on-treatment peak AST/ALT may or may not happen on the same day of liver testing.

- The analyses will be conducted using the 30-day safety window and repeated using the 100-day safety window.
- A by-subject listing of these specific abnormalities will be provided.

Abnormal Thyroid Function Test

The number of subjects with the following laboratory abnormalities from on-treatment evaluations will be summarized for all treated subjects, and by cohorts and by SRT status:

- TSH value > ULN and
 - with baseline TSH value \leq ULN
 - at least one FT3/FT4 test value < LLN
 - with all other FT3/FT3 test values \geq LLN
 - with FT3/FT4 test missing
- TSH < LLN and
 - with baseline TSH value \geq LLN
 - at least one FT3/FT4 test value > ULN
 - with all other FT3/FT3 test values \leq LLN
 - with FT3/FT4 test missing

The analyses will be conducted using the 30-day safety window and repeated using the 100-day safety window.

A by-subject listing of these specific abnormalities will be provided.

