Procedure	Cycle 1 and Cycle 2 (Cycle = 6 weeks)						Notes • Tumor assessment should be continued as per protocol even if dosing is delayed
	Day 1 Week 1	Day 1 Week 2	Day 1 Week 3	Day 1 Week 4	Day 1 Week 5	Day 1 Week 6	
Safety Assessments							
Targeted Physical Examination Cycle 1	X	X	X	X	X	X	Cycle 1: Weekly for first 6 weeks: conducted by study physician; Within 72 hours prior to dosing on Weeks 1 and 4.
Cycle 2	X			X			Cycle 2: Weeks 1 and 4: conducted by study physician within 72 hours prior to dosing.
Phone assessment with study medical staff: Cycle 2 only.		X	X		X	X	Cycle 2: Weeks 2,3,5,6 * Phone assessment with study medical staff required
Vital Signs and Oxygen Saturation Cycle 1	X	X	X	X	X	X	Including BP, HR, temperature, and oxygen saturation by pulse oximetry. Pulse oximetry at rest and after exertion prior to dosing. Cycle 1: Weekly for first 6 weeks.
Cycle 2	X			X			Cycle 2: Weeks 1 and 4 only
Physical Measurements (including performance status) Cycle 1	X	X	X	X	X	X	Weight and ECOG status within 72 hours prior to dosing. Cycle 1: Weekly for first 6 weeks.
Cycle 2	X			X			Cycle 2: Weeks 1 and 4 only
Adverse Events Assessment	Continuously						
	■	■	■	■	■	■	
	■	■	■	■	■	■	

Table 5.1-2: On-study Assessments Cycles 1 and 2 Only (CA209204)							
Procedure	Cycle 1 and Cycle 2 (Cycle = 6 weeks)						Notes • Tumor assessment should be continued as per protocol even if dosing is delayed
	Day 1 Week 1	Day 1 Week 2	Day 1 Week 3	Day 1 Week 4	Day 1 Week 5	Day 1 Week 6	
Laboratory Tests	X			X			Within 72 hrs prior to dosing to include CBC w/differential, LFTs, BUN or serum urea level, creatinine, Ca, Mg, Na, K, Cl, LDH, Glucose, amylase, lipase, TSH (with reflexive Free T4 and Free T3)
Pregnancy Test (WOCBP Only)	X			X			Within 24 hours prior to administration of study drug. Serum or Urine
[REDACTED]	[REDACTED]						[REDACTED]
[REDACTED]							[REDACTED]
[REDACTED]			[REDACTED]				[REDACTED]
[REDACTED]			[REDACTED]				[REDACTED]
[REDACTED]			[REDACTED]				[REDACTED]
[REDACTED]			[REDACTED]				[REDACTED]

Table 5.1-2: On-study Assessments Cycles 1 and 2 Only (CA209204)							
Procedure	Cycle 1 and Cycle 2 (Cycle = 6 weeks)						Notes • Tumor assessment should be continued as per protocol even if dosing is delayed
	Day 1 Week 1	Day 1 Week 2	Day 1 Week 3	Day 1 Week 4	Day 1 Week 5	Day 1 Week 6	
Efficacy Assessments							

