5.3.7 Laboratory Test Assessments

Results of all safety laboratory collections must be obtained and reviewed in advance of study drug dosing, as applicable. Amylase and lipase should be collected with the chemistry collection, but these lab results do not require review prior to dosing.

Serum Chemistry is to be obtained as specified in [Table 5.1-1](#) to [Table 5.1-4](#). A free-T4 and free-T3 will be performed reflexively for out of range TSH values. A CBC with differential is to be obtained. The CBC with differential includes hemoglobin, hematocrit, white blood cells, platelets (direct platelet count), erythrocyte sedimentation rate, WBC differential enumeration of total and percentage of neutrophils, lymphocytes, eosinophils, basophils and monocytes.

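### In the SAP's thyroid table the remainder row for low TSH uses the wrong limit (≤ LLN instead of ≤ ULN), so low TSH with normal free hormones has no free-hormone row

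*SAP*

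**What the plan says.** The part of SAP 7.6.12.4 (Additional Analyses) on abnormal thyroid function tests sets out two parallel blocks. Each has a baseline-TSH row and three free-hormone rows: abnormal, remainder and missing.

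- High TSH, headed "TSH value > ULN and": the abnormal row is "at least one FT3/FT4 test value < LLN" and the remainder row is "with all other FT3/FT3 test values \geq LLN".
- Low TSH: the abnormal row is "at least one FT3/FT4 test value > ULN" and the remainder row is "with all other FT3/FT3 test values \leq LLN".

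The summary is produced for all treated subjects, by cohort and by SRT status, with a 30-day and again with a 100-day safety window. A by-subject listing accompanies it.

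Protocol 5.3.7 says when the free hormones are measured: "A free-T4 and free-T3 will be performed reflexively for out of range TSH values". The on-study laboratory rows in Protocol 5.1 agree: "TSH (with reflexive Free T4 and Free T3".

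**The concern.** The two blocks are built as mirror images. In the first, the remainder row is the exact complement of the abnormal row. In the second, the inequality was reversed but the limit was not changed from LLN to ULN. The remainder row therefore covers only free hormones at or below the lower limit, and nothing covers values above LLN and up to ULN when no value is high.

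That gap removes the group the row is there to show: low TSH without raised free hormones, set against low TSH with them. The missing row is not meant to hold these subjects, because the protocol triggers both free-hormone tests whenever TSH is out of range. If the rule is programmed as printed, the three free-hormone rows fall short of the low-TSH total whenever such a subject occurs, in every presentation of the table. The plan has a stated interest in thyroid safety: thyroid disorder is a select-AE subcategory (SAP Table 11-3), and hypothyroidism/thyroiditis and hyperthyroidism are named immune-mediated events (SAP 7.6.11).

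**Working it through.** The plan gives no figure to reproduce. The check is whether the free-hormone rows place every possible result exactly once.

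**Inputs.** The row definitions in SAP 7.6.12.4. FT3 and FT4 are each classed as low (L), normal (N) or high (H), which gives 3 × 3 = 9 patterns when both are measured. Two conventions apply: FT3/FT3 is read as FT3/FT4, as the neighbouring rows print it, and a value exactly equal to LLN satisfies ≤ LLN, so in the low-TSH block N means above LLN and up to ULN.

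**Counts.**

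- At least one value in a given extreme class: 9 − 2 × 2 = 5 patterns. This applies both to any < LLN and to any > ULN.
- No value < LLN (both N or H): 2 × 2 = 4.
- Both ≤ LLN: 1, namely L/L.
- Both ≤ ULN (both L or N): 2 × 2 = 4.

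| Block | Abnormal row | Remainder row | Placed | No row | Counted twice |
|---|---|---|---|---|---|
| High TSH, as written | 5 | 4 | 9 of 9 | 0 | 0 |
| Low TSH, as written | 5 | 1 | 6 of 9 | 3 | 0 |
| Low TSH, with ≤ ULN | 5 | 4 | 9 of 9 | 0 | 0 |

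The three unplaced patterns (FT3/FT4) are N/N, L/N and N/L. L/L is in the remainder row before and after the change.

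**One test missing.** Suppose the rows are applied to whichever values are available, and the missing row means both tests are absent. There are then 4 × 4 = 16 states. The high-TSH block leaves none unplaced. The low-TSH block as written leaves 5: the three above, plus one normal value with the other missing, in either order. With ≤ ULN it leaves none.

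**FT3/FT3 taken literally.** If the remainder row tests FT3 alone, the low-TSH block still leaves 2 of 9 patterns without a row, N/N and N/L. The high-TSH block then counts N/L and H/L twice.

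**The case against.** The strongest reply is that this is an obvious slip with little consequence. A programmer who sees a correct mirror block beside it would probably use ULN anyway. The SAP places its safety programming conventions in a core safety SAP (section 8) and the full list of analyses in a Data Presentation Plan (section 9), and neither is available here, so a misclassified table is possible but not shown. That stands as a limit on likelihood. It does not excuse the text: a silent correction would leave the output at odds with the SAP, with no record of why.

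The count of three is also not strictly literal, since it corrects FT3/FT3 while keeping ≤ LLN. That is fair, and the fully literal count is two. Low TSH with both free hormones normal has no row on either reading.

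Next, the SAP does not say that the rows must add to the block total. Nor does it link free-hormone results in time to the abnormal TSH, or say how to treat several abnormal TSH results in one subject. The hepatic rows in the same section do give windows of 1 day and 30 days. This stands too: changing the limit closes the gap between result patterns but does not settle timing.

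Finally, ≤ LLN might have been intended, to isolate low TSH with low free hormones. That does not fit a row worded as covering all other values, it breaks the mirror with the first block, and it would still leave normal free hormones without a row.

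**Conclusion.** The row is wrong as written. With FT3/FT3 read as FT3/FT4 and both tests available, the low-TSH block places 6 of 9 result patterns, where the high-TSH block places 9 of 9. Using ≤ ULN restores 9 of 9 with no overlap. The mismatch lies in the letters LLN and not in a symbol, so a PDF reading error is unlikely, and no other section of the SAP or protocol redefines the row.

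This is a drafting error in a programming rule with a narrow effect. Affected subjects still count under the low-TSH heading, in the row "with baseline TSH value \geq LLN" where they qualify, and in the by-subject listing. Efficacy results and the select-AE and immune-mediated AE counts do not change. How many subjects are affected cannot be derived from the documents and could be zero. It is worth correcting, at low priority.

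**What to change.** In SAP 7.6.12.4, in the low-TSH block, change the limit in the remainder row from LLN to ULN, so that it covers all other FT3/FT4 values at or below ULN. In the remainder row of both blocks, correct FT3/FT3 to FT3/FT4; this second change is editorial. Then check that the table program uses the corrected limit in all presentations: overall, by cohort, by SRT status and in both safety windows.

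The cost is three text corrections in one section (one limit, two test names) and a program check. No new data are needed.

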7.6.13 Vital Signs

Vital signs consist of blood pressure, heart rate, respiratory rate and temperature measurements will be summarized and listed for all treated subjects. Summaries of vital signs will be provided for each parameter. The actual values by visit, and changes from baseline for post-baseline visits will be summarized by cohorts and by SRT status.

A summary table on weight reduction (Reduction \geq 5%, None) based on last measurement will also be presented by cohorts and by SRT status.

A by-subject listing of all vital signs will be provided. Subjects with vital signs out of pre-specified range will also be listed.

The following criteria will be used to determine vital sign results that are outside of a pre-specified range, where changes from baseline are based on matched postural positions and are calculated as parameter value - baseline parameter value:

Table 3: Out-of-Range Vital Sign Criteria

Heart Rate(bpm)	Value > 100 and change from baseline > 30, or Value < 55 and change from baseline < -15
Systolic BP(mmHg)	Value > 140 and change from baseline > 20, or Value < 90 and change from baseline < -20
Diastolic BP(mmHg)	Value > 90 and change from baseline > 10, or Value < 55 and change from baseline < -10
Respiration(breaths/min)	Value > 16 or change from baseline > 10
Temperature (°C)	Value > 38.3°C or change from baseline > 1.6°C

7.6.14 Electrocardiogram

By-subject listing of ECG test results will be provided for all treated subjects.

7.6.15 Physical Examination Findings

All abnormal physical examination findings will be listed per subject and visit for all treated subjects.

7.6.16 Pregnancy

By-subject listing of pregnancy tests results will be provided for all treated female subjects.

[REDACTED]

expression as a predictive biomarker, including selection of an optimal PD-L1 expression cut-off

[REDACTED]

[REDACTED]

[REDACTED]

[REDACTED]

[REDACTED]

[REDACTED]

[REDACTED]

[REDACTED]

[REDACTED]

[REDACTED]

[REDACTED]

[REDACTED]

[REDACTED]

[REDACTED]

[REDACTED]

[REDACTED]

[REDACTED]

[REDACTED]

[REDACTED]

[Redacted text block]

[Redacted text block]

[Redacted text block]

[Redacted text block]

[Redacted text block]

[Redacted text block]

[Redacted]

[Redacted]

[Redacted]

[Redacted]

[Redacted]

[Redacted]

[Redacted]

[Redacted]

[Redacted]

8 CONVENTIONS

All statistical analyses will be carried out using SAS (Statistical Analysis System software, SAS Institute, North Carolina, USA) unless otherwise noted.

Safety conventions from Programming are summarized in the core safety SAP.

8.1.1 *Decimal Places*

The number of decimal places displayed in all listings will be determined by the number of decimal places in the raw data.

Unless otherwise specified, minimum and maximum will be reported to the precision as the data collected, one more decimal place for the mean and median, and two more decimal places for the standard deviation. The adjusted geometric mean, geometric mean ratio and the lower and upper limits of confidence interval will be displayed to three decimal places.

8.1.2 Partial Date Imputation

The following conventions may be used for imputing partial dates for analyses requiring dates:

For missing and partial AE onset dates, imputation will be performed using the Adverse Event Domain Requirements Specification. Missing and partial Non-Study Medication Domain dates will be imputed using the derivation algorithm described in BMS Non-Study Medication Domain Requirements Specification.

For death dates, the following conventions will be used for imputing partial dates:

- If only the day of the month is missing, the 1st of the month will be used to replace the missing day. The imputed date will be compared to the last known date alive + 1 day and the maximum will be considered as the death date.
- If the month or the year is missing, the death date will be imputed as the last known date alive + 1 day
- If the date is completely missing but the reason for death is present the death date will be imputed as the last known date alive + 1 day
- For date of progression, the following conventions will be used for imputing partial dates:
- If only the day of the month is missing, the 1st of the month will be used to replace the missing day*.
- If the day and month are missing or a date is completely missing, it will be considered as missing.
- * In case, the date of death is present and complete, the imputed progression date will be compared to the date of death. The minimum of the imputed progression date and date of death will be considered as the date of progression.
- For other partial/missing dates, the following conventions will be used:
- If only the day of the month is missing, the 15th of the month will be used to replace the missing day.
- If both the day and the month are missing, “July 1” will be used to replace the missing information.
- If a date is completely missing, it will be considered as missing.

The following conversion factors will be used to convert days to months or years: 1 month = 30.4375 days and 1 year = 365.25 days.

Duration (e.g. time from first diagnosis of Non-small Cell Lung Cancer (NSCLC) to first dosing date, duration response, and time to response) will be calculated as follows:

$$\text{Duration} = (\text{Last date} - \text{first date} + 1)$$

Last known date alive will be defined based on all appropriate dates collected on the CRF.

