Tumor Assessment	
Section 5.4 CT/MRI of chest, abdomen, pelvis, and brain (MRI). FIRST tumor assessment should first be performed at 6 weeks (± 7 days) from first dose date. SUBSEQUENT tumor assessments should occur every 6 weeks (± 7 days) up to first 12 months (week 48), then every 12 weeks (± 7 days) until documented disease progression.
						
	■	■	■	■	■	■	
	■			■			
Administer Study Treatment							
Nivolumab 1mg/kg + Ipilimumab 3 mg/kg	X			X			Dose will remain the same as long as current patient weight is within 10% of the Cycle 1/Day 1/enrollment weight Doses may be administered within 2 days after the scheduled date if necessary. See Section 4.5.2.1 for dose interruption specific for SRT.

Table 5.1-3: On-study Assessments Cycle 3 and Beyond (CA209204)							
Procedure	Cycle 3 and Beyond (Cycle = 6 weeks)						Notes
	Day 1 Week 1	Day 1 Week 2	Day 1 Week 3	Day 1 Week 4	Day 1 Week 5	Day 1 Week 6	
Safety Assessments							
 Tumor assessment should be continued as per protocol even if dosing is delayed. Subjects may continue to receive treatment for a maximum of 24 months from the Date of the First Treatment with Nivolumab +Ipilimumab.
Targeted Physical Examination	X		X*		X		Week 1 and Week 5: conducted by study physician. *Week 3: conducted by study medical staff. May be performed more frequently as clinically indicated
Vital Signs and Oxygen Saturation	X		X		X		Including BP, HR, temperature, and oxygen saturation by pulse oximetry. Pulse oximetry at rest and after exertion prior to dosing.
Physical Measurements and Performance Status	X		X		X		Weight and ECOG status within 72 hours prior to dosing.
Adverse Event Assessment	Continuously						
████████████████████	█		█		█		████████████████████
Laboratory Tests	X				X		Within 72 hrs prior to dosing to include CBC w/differential, LFTs, BUN or serum urea level, creatinine, Ca, Mg, Na, K, Cl, LDH, Glucose, amylase, lipase, TSH (with reflexive Free T4 and Free T3)
Pregnancy Test (WOCBP Only)	X				X		Within 24 hours prior to administration of study drug. Serum or Urine
████████████████████	█						████████████████████

Table 5.1-3: On-study Assessments Cycle 3 and Beyond (CA209204)							
Procedure	Cycle 3 and Beyond (Cycle = 6 weeks)						Notes
	Day 1 Week 1	Day 1 Week 2	Day 1 Week 3	Day 1 Week 4	Day 1 Week 5	Day 1 Week 6	

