 - if the radiographic progression date is prior to or equal to the minimum of complete response date and partial response date, change BOR to PD;
 - if BOR is CR and both the complete response date and partial response date are non-missing and radiographic progression date is between those two, change BOR to PR.

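### SAP 8.1.2 lets an imputed progression date fall before a scan without progression, and leaves a progression known only by year with no usable date for PFS

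*SAP*

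**What the plan says.** SAP 8.1.2 writes out rules for three classes of partial date, introduced by "The following conventions may be used for imputing partial dates for analyses requiring dates".

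- **Progression, day missing:** "If only the day of the month is missing, the 1st of the month will be used to replace the missing day". A footnote adds one check, for subjects with a complete date of death: "The minimum of the imputed progression date and date of death will be considered as the date of progression".
- **Progression, day and month missing:** "If the day and month are missing or a date is completely missing, it will be considered as missing".
- **Death, day missing:** also the 1st of the month, but "The imputed date will be compared to the last known date alive + 1 day and the maximum will be considered as the death date". A death whose month or year is unknown is kept and dated one day after the last known date alive.
- **Other dates:** the 15th if only the day is missing, and 1 July if day and month are missing.

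Two parts of the SAP use the progression date. Table 7.5.2.8-1 dates a PFS event at the first documented progression. SAP 4.1 uses the radiographic progression date to adjust BOR for the primary analysis. NE, or SD of under 6 months, becomes PD only if that date is non-missing. For a CR or PR with a preceding PD, the rule is: "if the radiographic progression date is prior to or equal to the minimum of complete response date and partial response date, change BOR to PD". Neither section says whether imputed dates are excluded.

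**The concern.** The death rule protects against an impossible order of events and the progression rule does not. Its one check has no practical effect: the 1st of the month is never later than the true progression, and the true progression is never later than death, so the ceiling does not bind in a consistent record. Nothing stops the imputed date from falling before a scan on which the investigator recorded response or stable disease.

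The month-missing rule has a different fault. Of the three classes, only progression discards a year that is known. A subject who is known to have progressed is left without a date, and the PFS table has no row for that case.

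At stake are the event times, and for year-only records the event status, in intracranial, extracranial and global PFS. There is a weaker link to the adjusted BOR.

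**Working it through.** The plan gives no figure for partial dates, so there is none to reproduce.

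**Inputs.** Scans are every 6 weeks (42 days), each ±7 days, to week 48 (protocol Table 5.1-2). A response is confirmed by MRI about 4 weeks (28 days) later (protocol 5.4.3). Extra MRIs are allowed as medically indicated (protocol 5.4.2). A PR needs two determinations at least 4 weeks apart before progression (protocol 8.3.1.1). Assumption: progression is equally likely on any day of a four-year calendar (1,461 days, 48 months).

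**1. Size of the shift.** Shift = day of month − 1. The mean is 14.7 days early and the maximum 30.

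**2. Imputed date before the previous scan.** With a gap of g days between that scan and progression, this happens when day − 1 > g, that is, day ≥ g + 2.

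| Gap (days) | Days of month affected | Share |
|---|---|---|
| 7 | 9th onward | (1,461 − 48×8)/1,461 = 73.7% |
| 14 | 16th onward | (1,461 − 48×15)/1,461 = 50.7% |
| 21 | 23rd onward | (1,461 − 48×22)/1,461 = 27.7% |
| 28 | 30th, 31st | (44 + 28)/1,461 = 4.9% |
| 29 | 31st | 28/1,461 = 1.9% |
| 30 or more | none | 0% |

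The 14-day gap arises in ordinary conduct: a confirmatory MRI at 28 days leaves 42 − 28 = 14 days to the next scheduled scan. Moving that scan by its ±7 days gives 7 to 21. Two scheduled scans at the nominal 42 days are not exposed. At the closest spacing the windows allow, 42 − 14 = 28 days, 4.9% are.

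**3. Example.** PR on 12 April, confirmed on 10 May, PD on 24 May recorded as May only. The imputed date is 1 May, so PFS ends 23 days before the true progression and 9 days before a scan that showed response.

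**4. Effect on a confirmed response.** The SAP 4.1 adjustment compares progression with the first response date. For a confirmed response, PD comes at least 28 + 1 = 29 days after that date. The imputed date is on or before first response when day − 1 ≥ gap:

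- 29 days: PD on the 30th or 31st, 72/1,461 = 4.9%
- 30 days: PD on the 31st, 28/1,461 = 1.9%
- 31 days or more: 0%

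An instance is PR on 2 May, confirmed on 30 May, PD on 31 May, imputed 1 May. In the step 3 example, 1 May is after 12 April and the PR stands.

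**5. Year-only progression.** Against Table 7.5.2.8-1, the documented-progression row needs a date that no longer exists. The row for no progression and no death does not describe this subject either. The natural fallbacks are:

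- alive: censored at the last evaluable assessment;
- new therapy started: censored at the last evaluable assessment before it;
- died without earlier new therapy: event at the date of death.

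The first two drop a known event and the third delays it. All lengthen PFS.

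**6. Year-only progression and BOR.** A missing date switches off the NE-to-PD and SD-to-PD adjustments. This changes the BOR table and can change who is response-evaluable (SAP 6.3). It does not by itself change CBR, because NE, SD under 6 months and PD all count as no benefit.

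**The case against.** The strongest reply is that the affected set may be empty. PFS excludes clinical progression, so a progression is a scan result. Scan dates are normally complete, and all images go to a core laboratory. A radiographic progression known only to the year is improbable. This stands, and it limits the point to a small correction.

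Second, censoring of year-only progressions is inferred, because the SAP is silent. That is also correct, and the silence is itself part of the defect.

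Third, using the 1st of the month shortens PFS, which is the cautious direction in a single-arm trial. The year-only rule works the other way, and opposite errors on different records need not cancel. Caution also does not justify a progression dated before a scan that contradicts it.

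Fourth, CBR is also analysed on BOR as entered in the CRF, and BICR-assessed CBR, ORR and PFS are sensitivity analyses. These give context but leave the investigator-assessed PFS dates uncorrected.

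Three stronger readings are tempting, and the documents do not support them:

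- **A PR followed within days or a couple of weeks by a day-missing PD is stripped from CBR and ORR.** Such a PR is unconfirmed. Protocol 5.4.3 and 8.3.1.1 and SAP 4.1 require confirmation, so there is no valid response to lose.
- **The 51% is a rate of lost responses, because the confirming scan falls after the imputed date.** SAP 4.1 starts from the BOR entered in the CRF and compares progression with the first response date, not the confirming scan. The adjustment also requires a preceding PD, which even in the corner case only the imputed date would supply.
- **SD of just over 6 months is pulled below the threshold.** This needs duration of SD to end at the imputed progression date, and the SAP does not define it so.

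**Conclusion.** The point holds as a fault in the date rules for PFS, of minor weight. A day-missing progression date is on average 14.7 days early. It precedes the last scan without progression in about 51% of records with a 14-day gap (28% to 74% for gaps of 21 to 7 days), 4.9% at 28 days and none from 30 days. A year-only progression has no usable date and on the natural reading lengthens PFS.

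The link to the primary endpoint is confined to a confirmed response followed by PD 29 to 30 days after first response and dated the 30th or 31st. No general loss of CBR or ORR is shown.

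The percentages assume a uniform day of progression and apply only to records with the day missing. The documents do not say how many such records exist, and there may be none, so the effect on the reported PFS cannot be stated.

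**What to change.** In SAP 8.1.2, for progression dates:

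1. Use the scan date of the assessment that showed PD.
2. If that is incomplete but the month is known, use the later of the 1st of the recorded month and the day after the last evaluable assessment without PD, capped at the date of death.
3. If the month is missing, keep the event at the later of 1 January of the recorded year and the day after the last evaluable assessment without PD, capped at the date of death.

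Add a matching row to Table 7.5.2.8-1 for documented progression with an incomplete date. State whether imputed dates feed the SAP 4.1 adjustments, make the conventions binding instead of permissive, and report the number of imputed progression dates by compartment.

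In the step 3 example, if the scan date could not be recovered, the date becomes the later of 1 May and 11 May, that is 11 May, after the confirming scan. The share of imputed dates that precede the last scan without progression falls to zero by construction.

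The cost is a few SAP sentences modelled on the existing death-date rule and one table row. No new data are needed, and sample size and power do not change.

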3.6.2 Lost to Follow-Up

All reasonable efforts must be made to locate subjects to determine and report their ongoing status. This includes follow-up with persons authorized by the subject as noted above. Lost to follow-up is defined by the inability to reach the subject after a minimum of three documented phone calls, faxes, or emails as well as lack of response by subject to one registered mail letter. All attempts should be documented in the subject's medical records. If it is determined that the subject has died, the site will use permissible local methods to obtain the date and cause of death.

If investigator's use of third-party representative to assist in the follow-up portion of the study has been included in the subject's informed consent, then the investigator may use a Sponsor-retained

third-party representative to assist site staff with obtaining subject's contact information or other public vital status data necessary to complete the follow-up portion of the study. The site staff and representative will consult publicly available sources, such as public health registries and databases, in order to obtain updated contact information. If after all attempts, the subject remains lost to follow-up, then the last known alive date as determined by the investigator should be reported and documented in the subject's medical records.

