4.2 Secondary Endpoints

- Intracranial objective response rate (ORR) and intracranial progression free survival (PFS) per modified RECIST 1.1 criteria.
- Extracranial CBR, extracranial ORR, extracranial PFS per RECIST 1.1 criteria
- Global (intracranial +extracranial) CBR, global ORR, and global PFS per a combination of modified RECIST 1.1 criteria for intracranial lesions and RECIST 1.1 for extracranial disease.
- Overall survival (OS)

[figure not shown]
- Safety and tolerability will be measured by the incidence of AEs, serious adverse events (SAE), deaths, and laboratory abnormalities.

ORR is defined as the number of subjects who achieve a best overall response (BOR) of complete response (CR) or partial response (PR) divided by the number of treated subjects.

PFS is defined as the time between the date of first study dose and the first date of documented progression, as determined by the investigator, or death due to any cause, whichever occurs first. Subjects who die without a reported progression will be considered to have progressed on the date of their death. Subjects who did not progress or die will be censored on the date of their last evaluable tumor assessment. Subjects who did not have any on study tumor assessments and did not die will be censored on their date of randomization. Subjects who started subsequent anti-cancer therapy without a prior reported progression will be censored on the date of their last evaluable tumor assessment prior to the initiation of subsequent anti-cancer therapy.

OS is defined as the time from first dosing date to the date of death and will be estimated using the Kaplan-Meier product-limit method, with subjects censored at their last known date alive.

[REDACTED]

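### A death recorded by year only is imputed to the day after the last known date alive, so where the recorded year is later the imputed date contradicts the record and shortens OS

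*SAP*

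**What the plan says.** SAP 8.1.2 gives three rules for incomplete death dates.

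- Day missing: "If only the day of the month is missing, the 1st of the month will be used to replace the missing day". A safeguard follows: "The imputed date will be compared to the last known date alive + 1 day and the maximum will be considered as the death date".
- Month or year missing: "If the month or the year is missing, the death date will be imputed as the last known date alive + 1 day". No comparison step is given.
- Whole date missing: "If the date is completely missing but the reason for death is present the death date will be imputed as the last known date alive", plus 1 day.

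For partial dates other than death and progression, the same section keeps a known year: "If both the day and the month are missing, “July 1” will be used to replace the missing information".

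The anchor date comes from the case report form: "Last known date alive will be defined based on all appropriate dates collected on the CRF". SAP 4.2 then uses the death date directly: "OS is defined as the time from first dosing date to the date of death". SAP 4.2 and Table 7.5.2.8-1 also make the death date the PFS event date when no progression was reported.

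**The concern.** A death recorded only as a year has its month missing, so the second rule applies. That rule makes no use of the year and gives the same answer as a completely missing date. The day-missing rule works differently: it takes the earliest date the record allows and never places a death before the recorded month. The year-only rule has no such floor and can place a death in a calendar year before the recorded one. Nothing else in the SAP or protocol corrects this.

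At stake are the OS estimates (median and fixed-time rates, SAP 7.5.2.3) and PFS for subjects who die without reported progression (SAP 7.5.2.8). The landmark survival analyses in SAP 7.5.2.4 and 7.5.2.5 are also exposed, because they drop subjects who die before the landmark, and a death dated too early could remove someone who was alive at that time.

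**Working it through.** The plan states no figure on this point, so there is none to reproduce. The check applies the rules to assumed dates.

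**Inputs**
- Imputation rules: SAP 8.1.2, as above.
- Survival contacts: every 3 months, window 7 days either side (Protocol Table 5.1-4, footnote b).
- Conversion: 30.4375 days per month (SAP 8.1.2).
- Assumed: the dates in the table. The documents do not report any partial death dates.

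**Formulas.** Let L be the last known date alive and Y the recorded year of death.
- SAP rule: L + 1 day.
- The SAP's day-missing logic carried up to the year (the floored date): the later of 1 January of Y and L + 1 day.
- Provable shortening: 1 January of Y minus (L + 1 day), or 0 if that is negative.

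| L | Y | SAP date | Floored date | Provable shortening |
|---|---|---|---|---|
| 15-Jun-2018 | 2019 | 16-Jun-2018 | 1-Jan-2019 | 199 days (199/30.4375 = 6.5 months) |
| 15-Mar-2017 | 2018 | 16-Mar-2017 | 1-Jan-2018 | 291 days (9.6 months) |
| 1-Oct-2017 | 2018 | 2-Oct-2017 | 1-Jan-2018 | 91 days (3.0 months) |
| 25-Sep-2017 | 2018 | 26-Sep-2017 | 1-Jan-2018 | 97 days (3.2 months) |
| 15-Mar-2017 | 2017 | 16-Mar-2017 | 16-Mar-2017 | 0 |

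**Limit under scheduled contact.** The fourth row is the limiting case, counting from the previous actual contact. Three months after 25-Sep-2017 is 25-Dec-2017, and the 7-day window ends on 1-Jan-2018. The provable shortening is therefore at most about 97 days. If the earlier contact was itself made up to 7 days ahead of the nominal calendar, the limit rises by up to 7 days. Larger values, as in the first two rows, need missed contacts.

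**What the correction recovers.** In the first row the true death date lies between 1-Jan-2019 and 31-Dec-2019. The SAP date is therefore 199 to 563 days early (199 + 364 = 563). The floored date is still 0 to 364 days early. The difference is 199 days wherever in 2019 the death fell, and only that part is provable and correctable.

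**Fixed-time rates.** These run on time from first dose, not on calendar year. Assume a first dose on 1-Nov-2016 and use the SAP's duration convention (last minus first plus 1).
- L = 1-Oct-2017, Y = 2018: the SAP rule gives 336/30.4375 = 11.04 months; the floored date gives 427/30.4375 = 14.03 months. The 12-month status is wrong under the SAP rule.
- L = 15-Nov-2017, Y = 2018: the SAP rule gives 381/30.4375 = 12.52 months, against 14.03. The imputed year is wrong, yet the 12-month status is unchanged.

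A rate changes only if the imputed and true survival times fall on opposite sides of the time point. With 110 subjects and no earlier censoring, one such death moves a rate by 1/110, about 0.9 percentage points.

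**The case against.** The best case against raising this is materiality.

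- **Frequency.** Three-monthly contact, sponsor-requested survival checks (Protocol 3.6) and the tracing steps in Protocol 3.6.2 should make year-only deaths rare. This stands. A reader might infer that tracing subjects lost to follow-up is known to yield year-only dates. The protocol does not support that. It says "the site will use permissible local methods to obtain the date and cause of death", which provides for finding deaths but does not say the dates are incomplete.
- **Size.** A reader might quote the full 563 days as the error. That is the far end of a range that is mostly uncertainty within the recorded year, and the correction leaves that uncertainty in place. The provable part is 199 days, in an assumed case.
- **Direction.** The first of the month and 1 January are also earliest-possible dates, so one-sided shortening is not unique to this rule. In a single-arm trial, shorter OS works against the treatment and cannot inflate the survival result. This stands.
- **Reach.** The primary endpoint is intracranial clinical benefit rate, and sample size and power rest on it alone. OS and PFS are secondary and estimated without a comparator. This stands.
- **Permissive wording.** The SAP introduces these conventions as ones that may be used. This carries little weight, because no alternative for death dates is given.

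None of this justifies a death date that the trial's own record contradicts.

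**Conclusion.** The point holds as a minor defect. As written, the rule discards a recorded year of death. Whenever that year is later than the year of the last known date alive plus 1 day, the imputed date is false, and OS (and PFS for deaths without reported progression) is shortened by at least the gap to 1 January of the recorded year. If both dates fall in the same calendar year, there is no contradiction and the correction changes nothing.

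The sizes rest on assumed dates, and the number of affected subjects is unknown and probably small. The documents do not support a reading that the OS results are materially biased, that survival is overstated, or that every change of calendar year alters a fixed-time rate.

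**What to change.** In SAP 8.1.2, replace the month-or-year rule for death dates with:

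*If the month is missing and the year is known, use 1 January of that year, compare with last known date alive + 1 day, and take the maximum; if the year is missing, use last known date alive + 1 day.*

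This carries the SAP's own day-missing logic up to the year. It costs one sentence and a small programming change, with no new data and no patients, and is best made before the final database lock. If the lock has already passed, listing any year-only death dates will show whether a rerun would change anything.
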